## Clinical Investigational Plan

### 3.0 RISKS AND BENEFITS OF THE CLINICAL STUDY

Subjects enrolled in this study will already have an implanted IPG programmed with burst stimulation as part of their standard pain management. In this study, we propose to evaluate alternative stimulation parameters that will deliver less current compared to the parameters already programmed in the stimulators. The subjects will not be required to discontinue or interrupt any current treatment prior to enrollment. During the study, the subjects will not be allowed access to the patient programmer and therefore will not be able to adjust therapy intensity. There is a possibility that the new stimulation parameters will not provide pain relief that is equivalent to the standard stimulation parameters, but optimal pain relief is expected to return on reuse of standard burst stimulation parameters. Although not expected, it is possible that the new stimulation parameters will instead improve pain relief. Use of these two new energy efficient stimulation parameters has the potential to prolong the battery life of a non-rechargeable, primary cell IPG by approximately 100% to 200%. It also has the potential to improve patient convenience by decreasing the frequency with which the patient has to recharge a non-primary cell IPG.

### 3.1 DESCRIPTION OF SUBJECT POPULATION

Up to 40 subjects will be enrolled in this study in up to 4 centers. Of these, it is expected that 30 subjects will be successfully screened and complete the study. Subject will be 18 years of age or older. Subjects will already have an implanted SJM spinal cord stimulator for control of chronic intractable pain associated with a diagnosis of failed back surgery syndrome or neuropathic back and/or leg pain. Subjects will be currently using burst stimulation for at least three month as part of their clinical care.

### 3.2 ANTICIPATED CLINICAL BENEFITS

There are no anticipated clinical benefits over conventional burst spinal cord stimulation. The use of the alternate stimulation paradigms has the potential to prolong the battery life of a non-rechargeable, primary cell IPG by approximately 100% to 200% or to improve patient convenience by decreasing the frequency with which the patient has to recharge a non-primary cell IPG.

### 3.3 ANTICIPATED ADVERSE EVENTS AND ADVERSE DEVICE EFFECTS

There are no anticipated adverse events and adverse device effects in conjunction with the burst microdosing stimulation parameters. There is a possibility that the new stimulation parameters will not provide pain relief equivalent to the standard stimulation parameters, but optimal pain relief is expected to return on reuse of standard burst stimulation parameters.

## Clinical Investigational Plan

### 3.4 RESIDUAL RISKS ASSOCIATED WITH THE DEVICE UNDER INVESTIGATION, AS IDENTIFIED IN THE RISK ANALYSIS REPORT

There are no residual risks associated with the stimulation protocol under investigation.

### 3.5 RISKS ASSOCIATED WITH PARTICIPATION IN THE CLINICAL STUDY

As the alternate stimulation parameters will deliver less current compared to the standard burst stimulation received by the subjects before enrolling in the study, there will not be any additional risk to the subjects beyond those associated with spinal cord stimulation and the potential reduction of therapeutic efficacy during burst microstimulation.

### 3.6 POSSIBLE INTERACTIONS WITH CONCOMITANT MEDICAL TREATMENTS AND/OR CONCURRENT MEDICAL INTERVENTIONS

There are no possible interactions with concomitant medical treatment and/or concurrent medical intervention beyond those associated with standard medical care using spinal cord stimulation.

### 3.7 STEPS THAT WILL BE TAKEN TO CONTROL OR MITIGATE THE RISKS

Subjects will be informed concerning the potential risks and benefits associated with participation in the study prior to their enrollment.

### 3.8 RISK-TO-BENEFIT RATIONALE

The study will use devices currently approved as part of standard pain management care. As the alternate stimulations parameters will deliver less current compared to the standard treatment received by the subjects before enrolling in the study, the only risk entailed by this study is represented by the possibility that the pain relief afforded by the alternative microdosing paradigm might be inferior to the one provided by standard burst stimulation. Sequestering the patient programmer will prevent the subjects from adjusting therapy and can represent an inconvenience to the subjects, but is necessary to ensure blinding of the subjects.

Establishing equivalency between standard burst stimulation and more energy efficient stimulation paradigm could lead to a prolonging battery life up to 200% and/or shorter time for IPG recharging. This will reduce IPG replacement surgeries in primary cell stimulators and increased patient convenience in rechargeable stimulators.

### 3.9 DESCRIPTION OF HISTORY OF MODIFICATIONS OR RECALL IN RELATION TO SAFETY AND CLINICAL PERFORMANCE FOR DEVICE UNDER INVESTIGATION

There have been no modifications or recalls in relation to safety and clinical performance of the devices utilized in this study.

## Clinical Investigational Plan

### 4.0 STUDY DESIGN

#### 4.1 PURPOSE

The purpose of this clinical study is comparing differences in therapeutic efficacy between conventional burst stimulation parameters (Burst train consisting of 5 pulses, Intraburst frequency: 500 Hz, Burst Rate: 40 Hz, Pulse width: 1000  $\mu$ s) to two energy efficient burst microdosing stimulation paradigms:

- Standard burst stimulation parameters with 5 seconds of STIM ON, followed by 5 seconds of STIM OFF
- Standard burst stimulation parameters with 5 seconds of STIM ON, followed by 10 seconds of STIM OFF

#### 4.2 STUDY DESIGN AND SCOPE

This clinical feasibility study is as a prospective, double-blinded, randomized, crossover, multicenter study designed to compare efficacy of different burst stimulation parameters.

Patients recommended by the Principal Investigator as a candidate and who meet the standard requirements will be approached to participate in this study. The patient will be informed about the study to determine if he/she is interested in participating. After the patient signs the informed consent, he/she will be screened according to the inclusion/exclusion criteria. If the patient meets the study criteria, he/she will continue as a subject in the study, whereas subjects who do not meet the inclusion/exclusion criteria will exit the study. Subjects' patient programmer will be sequestered and subjects will be randomized 1:1:1 to one of the three treatment sequences:

##### *Group 1:*

- Standard burst
- 5 seconds STIM ON, 5 seconds STIM OFF, standard burst parameters
- 5 seconds STIM ON, 10 seconds stim OFF, standard burst parameters

##### *Group 2:*

- 5 seconds STIM ON, 5 seconds STIM OFF, standard burst parameters
- 5 seconds STIM ON, 10 seconds stim OFF, standard burst parameters
- Standard burst

##### *Group 3:*

- 5 seconds STIM ON, 10 seconds stim OFF, standard burst parameters
- Standard burst
- 5 seconds STIM ON, 5 seconds STIM OFF, standard burst parameters

Subject's stimulators will be programmed with the first stimulation paradigm according to the group assignment. Stimulation intensity will gradually be increased until the subject perceives the stimulation to find the Threshold for Perception (TP), and then the intensity will subsequently be reduced to the sub-perception level providing optimal pain relief. Subjects will then receive a one-week pain diary to assess the pain levels during the first assigned stimulation

## Clinical Investigational Plan

paradigm. One week after this visit, the subject will be contacted to schedule the first follow up visit and instructed to start recording pain levels on the pain diary.

Two weeks after the screening visit, the subject will visit the clinic for the first follow up assessment. A Visual Analog Scale (VAS) score will be collected to determine pain levels during the first stimulation paradigm; the subject will also fill the EQ-5D and the satisfaction questionnaires administered by a clinician who is blinded to the stimulation paradigm. Subject's stimulators will be programmed with the second stimulation paradigm according to the group assignment. Stimulation intensity will gradually be increased until the subject perceives the stimulation to find the Threshold for Perception (TP), and then the intensity will subsequently be reduced to the sub-perception level providing optimal pain relief. Subjects will return the pain diary and will be provided with a new one for the assessment of the new stimulation paradigm. One week after this visit, the subject will be contacted to schedule the second follow up visit and instructed to start recording pain levels on the pain diary

Two weeks after the first follow up visit, the patient will return for the second follow up visit during which the efficacy of the second stimulation paradigm will be evaluated using the VAS, the EQ-5D and the subject satisfaction assessments administered by a clinician blinded to the stimulation paradigm. Subject's stimulators will be programmed with the third stimulation paradigm according to the group assignment. Stimulation intensity will gradually be increased until the subject perceives the stimulation to find the Threshold for Perception (TP), and then the intensity will subsequently be reduced to the sub-perception level providing optimal pain relief. Subjects will return the pain diary and will be provided with a new one for the assessment of the new stimulation paradigm. One week after this visit, the subject will be contacted to schedule the third follow up visit and instructed to start recording pain levels on the pain diary

Two weeks after the second follow up visit, the subject will return for the third follow up visit where the efficacy of the third stimulation paradigm will be assessed using the VAS, the EQ-5D and the subject satisfaction assessment. Subject will return the last pain diary and will be asked to specify their preference between the three different stimulation paradigms. After all activities are completed, the subject will exit the study.

Any unscheduled visits that occur within the study, and the reason for the visit will be documented. Stimulation related adverse events will be recorded throughout a subject's participation in the study.

The duration of each subject participation is expected to be between 6 and 8 weeks; the duration for the study is expected to be 6 months.

The clinical study will be conducted at a maximum of four centers in the European Union (EU).

An envelope-based system will be used for identifying which group the subject has been assigned. St. Jude Medical will provide sealed envelopes containing the site number and subject ID/sequence number. Inside the envelope, the randomization assignment will be identified along with the site number and subject ID/sequence number.

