### 4.4.2 Secondary Endpoint

Difference in:

- Quality of Life (EQ-5D)
- Subject satisfaction
- Subject preference
- Incidence rate of adverse events

between standard burst stimulation and the two burst microdosing paradigms.

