## Clinical Investigational Plan

### 6.4 FOLLOW UP VISIT 1

During the baseline visit, the investigator will collect the pain diary provided at the screening visit and record the current stimulation parameters in the parameters form. The subject will rate the pain during the first stimulation paradigm using the VAS, the EQ-5D and the satisfaction questionnaires administered by a clinician blinded to the stimulation paradigm. Subject’s stimulators will be programmed with the second stimulation paradigm according to the group assignment. Stimulation intensity will gradually be increased until the subject perceives the stimulation to find the Threshold for Perception (TP), and then the intensity will subsequently be reduced to the sub-perception level providing optimal pain relief. Subjects will be provided with a new pain diary for the assessment of the new stimulation paradigm. One week after this visit, the subject will be contacted to schedule the second follow up visit and instructed to start recording pain levels on the pain diary

The following activities and assessments will be performed during the first follow up visit.

Timing of visit	Activities at visit	Case Report Form
Follow up 1	
 
Collect pain diary
 
Programming parameters printout
 
Subject fills out pain assessment and quality of life questionnaires
 
Provide pain diary
 
Program IPG with second stimulation paradigm according to group assignment
 
	
 
VAS Form
 
EQ-5D Form
 
User Satisfaction Form
 
Parameters Form
 

### 6.5 FOLLOW UP VISIT 2

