### 8.2 PROCEDURE FOR ASSESSING, RECORDING, AND REPORTING ADVERSE EVENTS, DEVICE DEFICIENCIES/COMPLAINTS, ADVERSE DEVICE EFFECTS, SERIOUS ADVERSE EVENTS, AND SERIOUS ADVERSE DEVICE EFFECTS:

Safety surveillance within this study and the safety reporting both performed by the investigator, starts as soon as the subject is enrolled in this study (date of signature of the informed consent). The safety surveillance and the safety reporting will continue until the last investigational visit has been performed, the subject is deceased, the subject/investigator concludes his participation into the study or the subject/investigator withdraws the subject from the study, except as otherwise specified in the CIP.

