## Clinical Investigational Plan

All adverse event data including deaths will be collected throughout the clinical study and will be reported to the Sponsor on a dedicated case report form or through the EDC system. The Investigator will record all adverse events and device deficiencies on the appropriate case report forms.

Records relating to the subject's subsequent medical course must be maintained and submitted (as applicable) to the Sponsor until the event has subsided or, in case of permanent impairment, until the event stabilizes and the overall clinical outcome has been ascertained. Adverse events will be monitored until they are adequately resolved. The status of the subject's condition should be documented at each visit.

The investigator will report the event to the EC per their reporting requirements.

Reportable events to sponsor are considered:

- All Adverse Device Effects
- All Serious Adverse Events

All above events will be reported to the Sponsor, as soon as possible, but no later than 72 hours of first learning of the event.

There are no additional anticipated adverse events associated with the use of devices utilized in this study that are different than those currently identified for the commercially available neurostimulation systems.

Additional information may be requested, when required, by the Sponsor in order to support the reporting of AEs to regulatory authorities.

The investigator must notify the EC, if appropriate, in accordance with national and local laws and regulations, of the AEs reported to the Sponsor.

All adverse events will be reported as per applicable regulatory requirements.

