### 12.0 STATISTICAL CONSIDERATIONS

#### 12.1 STATISTICAL DESIGN, HYPOTHESES, METHOD AND ANALYTICAL PROCEDURES

During baseline visit subjects will be randomized 1:1:1 to one of the three treatment sequences. An envelope-based system will be used for identifying which group the subject has been assigned. St. Jude Medical will provide sealed envelopes containing the site number and subject ID/sequence number. Inside the envelope, the randomization assignment will be identified along with the site number and subject ID/sequence number.

During reprogramming the subjects will not be made aware of what paradigm is currently being programmed. Pain questionnaires (VAS, EQ-5D, satisfaction and stimulation preference) will be administered by a clinician blinded to the currently programmed stimulation paradigm.

Scores from the subject's questionnaires as well as subject satisfaction will be compared between follow up visits using a repeated measure ANOVA under the hypothesis of equivalence between standard and burst microdosing stimulation paradigms.

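### Section 4.2 narrows adverse event recording to stimulation-related events against section 8.2, and the comparison of adverse event incidence between paradigms is not shown to be protected by blinding

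*Combined protocol and SAP*

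**What the plan says.** **Endpoint.** Section 4.4.2 lists "Incidence rate of adverse events" among the secondary endpoints, compared between standard burst and the two microdosing paradigms. The synopsis does the same.

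**Scope of recording.** The last part of section 4.2 says that "Stimulation related adverse events will be recorded throughout" each subject's time in the study. Section 8.2 reads "The Investigator will record all adverse events and device deficiencies on the appropriate case report forms", and also "All adverse event data including deaths will be collected throughout the clinical study".

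**Who records.** Section 8.2 opens with "Safety surveillance within this study and the safety reporting both performed by the investigator". Under 6.4 and 6.5 the investigator is to "record the current stimulation parameters in the parameters form", and 6.6 asks the same at the third visit.

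**Who is blinded.** Section 12.1 says subjects are not told which paradigm is being programmed. It says the questionnaires, which it lists as VAS, EQ-5D, satisfaction and preference, "will be administered by a clinician blinded to the currently programmed stimulation paradigm". Adverse events are not on that list.

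**The concern.** The numerator of a comparative endpoint should follow one rule, and the person who fills it should not know the paradigm, or should have no discretion that matters. Neither condition is secured here.

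Under the wording of 4.2, an event counts only after someone has judged it stimulation-related. Under 8.2 it counts regardless. The same patients could therefore yield two different incidence figures.

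Under either rule, the recorder handles the programmed settings. The plan itself supplies an expectation that could colour the judgement: section 3.3 anticipates no adverse events with microdosing, and sections 3.5 and 3.8 argue that less current is delivered. That could make an aware investigator slower to ask about, or attribute, events under microdosing. The newness of the paradigm could equally draw more scrutiny to it, so the direction is not predictable.

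At stake is whether a difference in adverse event incidence, or the lack of one, can be read as a property of the paradigms.

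**Working it through.** The plan gives no adverse event rate, power or effect size (12.2 says power cannot be calculated), so there is no figure to reproduce. The check is mainly a comparison of texts.

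**Step 1: which scope governs?**

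- 4.2: stimulation-related events.
- Synopsis, Data Collection: occurrence of adverse events, with no relatedness limit.
- 8.1.2: the definition includes events unrelated to the device.
- 8.2: all adverse events, stated twice.
- 6.3, note before the visit table: from consent onward, reporting follows 8.2.

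Four places point to all events and one does not. The 72-hour list in 8.2 (adverse device effects and serious events) is an expedited subset, not a third scope. Section 4.2 is the outlier.

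**Step 2: is the recorder blinded?** Section 8.2 gives surveillance and recording to the investigator. Sections 6.4, 6.5 and 6.6 have the investigator record the current parameters. The paradigms differ in their on/off cycle, so a record of the settings would be expected to reveal the paradigm. Section 12.1 blinds the subject and the questionnaire clinician. No text blinds whoever elicits, records or judges adverse events.

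**Step 3: is there a scheduled enquiry?** Table 1 is presented as the full list of study-specific activities and has no adverse event row. The activity tables in 6.3 to 6.5 and the text of 6.6 have none either.

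**Step 4: what size could the distortion take?** All rates here are assumptions. Let p be the true proportion of subjects with an event in a period, equal under two paradigms, and let r1 and r2 be the fractions recorded. With n = 30 expected completers (12.2):

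- expected recorded count = n × p × r
- spurious difference = p × (r1 − r2)

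The plan names no test for adverse events. For illustration I used an exact two-sided McNemar test at 0.05, with the two periods treated as independent within subject. The discordant probabilities are b = p·r1·(1 − p·r2) and c = p·r2·(1 − p·r1). The number of discordant pairs is Binomial(30, b + c), split with probability b/(b + c).

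Example with p = 0.20, r1 = 1, r2 = 0.6: counts are 30 × 0.20 = 6.0 and 30 × 0.20 × 0.6 = 3.6. The difference is 0.20 × 0.4 = 8 points. b = 0.20 × 0.88 = 0.176 and c = 0.12 × 0.80 = 0.096.

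Each cell in the last three columns gives the recorded counts, the spurious difference in percentage points, and the chance of a false significant result (r1 = 1 throughout).

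| p | equal recording: false-positive chance | r2 = 0.8 | r2 = 0.6 | r2 = 0.4 |
|---|---|---|---|---|
| 10% | 1.0% | 3.0 v 2.4; 2; 1.1% | 3.0 v 1.8; 4; 1.6% | 3.0 v 1.2; 6; 2.6% |
| 20% | 2.2% | 6.0 v 4.8; 4; 3.1% | 6.0 v 3.6; 8; 6.5% | 6.0 v 2.4; 12; 14.2% |
| 30% | 2.5% | 9.0 v 7.2; 6; 4.3% | 9.0 v 5.4; 12; 11.4% | 9.0 v 3.6; 18; 27.6% |
| 50% | 2.8% | 15.0 v 12.0; 10; 7.7% | 15.0 v 9.0; 20; 25.8% | 15.0 v 6.0; 30; 58.6% |

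At 10% incidence the distortion is one or two subjects. It becomes material only if events are common and recording is markedly unequal.

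**The case against.** The strongest reply is that 8.2 plainly governs. The note in 6.3 refers sites there, 4.2 is a summary sentence that does not say recording is confined to related events, and under 8.2 the relatedness filter disappears. This largely stands: the conflict in scope is probably one misplaced qualifier. It does not answer the blinding gap, which exists under 8.2 as well.

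Three stronger readings are tempting, and the documents do not support them.

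- *Events enter the record only if subjects volunteer them.* Section 8.2 requires continuous surveillance and asks for the subject's condition to be documented at each visit. Section 6.7 provides for unscheduled visits with an adverse event form. The case report forms are held separately (Appendix H) and may already contain a prompt, an onset date and a relatedness field. What can be said is that the visit schedule does not specify how events are elicited.
- *The investigator is known to be unblinded because the investigator programs the device.* Section 6.6 says so only for the preferred paradigm at exit, after all three have been assessed. The earlier reprogramming is described without naming who does it. The support is the recording of parameters, and the investigator may mean more than one team member.
- *The plan assigns the relatedness decision to the investigator.* No text says this outright. It is an inference from the qualifier in 4.2 combined with 8.2.

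It is also fair to say that this is a feasibility study, that the endpoint is secondary, and that section 3.3 expects no adverse events from microdosing.

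**Conclusion.** The point holds in two limited parts. First, 4.2 contradicts 8.2, the synopsis and 8.1.2 on which adverse events are recorded. All-event recording is the likely intent, but the text should not leave an alternative numerator for a secondary endpoint. Second, even with all events recorded, nothing in the plan shows that elicitation and recording are done by someone unaware of the paradigm, so the label of a double-blinded study does not demonstrably extend to this endpoint.

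The documents do not fix the size. The tabulated range of 2 to 30 points rests entirely on assumed incidence and recording rates, and its lower end applies if events are rare. A reader might infer that centres will in fact diverge, or that the adverse event comparison is biased. The documents support neither; they show only that it is not protected. The correction is worth making because it is cheap, not because a large bias has been demonstrated.

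**What to change.** 1. In 4.2, delete the words limiting recording to stimulation-related events, so that it agrees with 8.2 and the synopsis. Keep relatedness as a separate field that does not decide whether an event is counted.
2. Add an adverse event row to Table 1 and to follow-up visits 1 to 3: one standard open question, asked by the blinded clinician who already administers the questionnaires, before any reprogramming or reading of parameters. Section 6.6 does not name that clinician, so state there that the rule in 12.1 applies at the third visit too.
3. Record the onset date and count each event under the paradigm programmed at onset, with a stated rule for events that begin on the day of a switch.

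The cost is protocol wording and one question at three existing visits, with no added visits or staff. The downside is a few more minor unrelated events to enter. The change does not by itself blind the relatedness field, which the investigator still needs for the 72-hour reporting in 8.2, but that field would no longer affect the incidence count.
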